# RESEARCH PLAN

### **BACKGROUND AND SIGNIFICANCE**

# Safe alternative nutritional supplementation is needed for atopic disorders suffered by US veterans:

Allergic Rhinitis a major condition impairing nasal health, effects 10-30% worldwide and 8% nationwide (1). A 10 year retrospective review revealed the majority of patients receiving care at the VA Greater Los Angeles Healthcare System (VAGLAHS) suffered from Allergic Rhinitis (2). From suffering comes cost, both indirect and direct. This can manifest as lost days of work and medication expense. Among atopic disorders, completed surveys determined allergic rhinitis as the highest cost in regards to both presenteeism and absenteeism, with the average total productivity loss per employee surveyed at 593 dollars per year (3). Over 3.4 billion dollars is spent directly treating allergic rhinitis, with 46.6% attributed to prescription medications. Despite no cost effective treatment for allergic rhinitis, nasal corticosteroids appear to be the most beneficial. Patients suffering from allergic rhinitis seek alternative therapies since 2/3rds report daily impairment from rhinitis symptoms despite the use of available medications (4).

#### The Association between Pollutants and Allergy:

The increase prevalence in allergic disorders may be attributable to pollutant factors (5). Bench Research led to a valid explanation of how pollutants can act as an adjuvant to allergens in susceptible patients. Original work discovered pollutant diesel exhaust particles (DEP) increase reactive oxygen species (ROS) in respiratory epithelium cells. This overabundance of oxidative stress leads increases intracellular nuclear factor kappa beta (NfKB) and Mitogen Activated Protein Kinase (MAP-kinase) cascades causing atopic cytokine production (6-9).

#### Animal Models investigating the association between Pollutants and Allergy:

Mice models validated the association between pollutant exposure and allergic response increase. Intranasal administration of diesel exhaust particles (DEP) caused an enhanced IgE response (10). More specifically administering DEP to dust mite sensitized mice enhanced the

production of dust mite specific IgE (11). Further experiments on mice solidified the concept that pollutants cause an increase allergic response when mice given DEP plus allergen were later found to have increased levels of atopic cytokines IL4 and IL5 within lungs and lymph nodes (12, 13).

# Human Models investigating the association between Pollutants and Allergy:

These findings were later replicated in human studies. Purified human B cells cultured with TH2 cytokines and DEP significantly increased IgE production when compared to B cells cultured with cytokines alone (14). Human studies demonstrated instillation of DEP through nasal lavage triggered an increase in nasal mucosa IgE production. (15). Nasal instillation of both DEP and ragweed produced increased atopic cytokines IL4, 5,6,10 and 13 and ragweed IgE 50 fold (16). Further review of these studies noted this increase in allergic biomarkers varied among individuals, with some having a drastic response and others no response (17).

# Phase II enzymes and Allergic Rhinitis:

The exaggerated atopic response from DEP when present with allergen exposure can be prevented by antioxidant production. Genetic polymorphisms in phase 2 antioxidant enzymes among individuals can determine how pollutants influence atopy. Endogenous anti-oxidant phase 2 enzymes GSTT1, GSTM1 and GSTP1 play a vital role in preventing the production of cytokines through restoration of redox balance between reduced and oxidized glutathione. Null genotypes for GSST1 and GSTM1 are more prevalent in atopic subjects (18), which could explain their diminished ability to produce phase II antioxidants leading to unchecked balance of oxidation. When exposed to pollutants, patients having null mutations in GST increase production of IgE and histamine levels respectively (19, 20). Patients with GST null mutations suffering from allergic rhinitis may respond best to antioxidant therapy.

# The use of antioxidants in treating Allergic Conditions:

Success rates in treating atopic conditions with antioxidants have been mixed (21-23). The importance of evaluating the patient for GST polymorphisms is supported by studies showing patients with GSTM1 null genotypes were more likely to have a greater detrimental loss of pulmonary function with exposure to ozone and a more positive response to consumption of Vitamin C/Vitamin E antioxidants supplementation (24, 25).

# Sulforaphane for treating allergic conditions:

The antioxidant Sulforaphane increases phase II enzyme production through activation of the Nrf2 transcription factor and the anti-oxidant response element (ARE) leading to an increase production of phase II enzymes (26-30). Sulforaphane also interferes with the pro-inflammatory pathways NkKB and AP1 responsible for the production of TH2 cytokines and IgE.

Sulforaphane has been shown to block B cell IgE production (31) and to inhibit IL8 production in human bronchial airway epithelial cell lines after exposure to DEP via inducing nuclear factor like 2, leading to enhanced Phase II enzyme production (32). A recent study showed that ova sensitized mice treated with SFN had a diminished inflammatory response after ova challenge leading to diminished hyper responsive airways (33).

# Broccoli Sprout for improving nasal health:

Broccoli sprouts (BSE), members of the cruciferous vegetable family, have extremely high concentrations of sulforaphane (26). The first placebo controlled BSE human study performed at our partnering institution involved administering escalating doses of broccoli sprout homogenate (BSH) to subjects. Phase II enzymes were shown to increase proportionally to the dose of BSE

given. Furthermore the induction of individual Phase II enzymes was inversely correlated with the expression of phase II enzymes (glutathione-s-transferase M1, glutathione-s-transferase P1, NADPH quinone oxidoreductase, and hemoxygenase-1) as revealed by genetic testing. Patients with GSTM1 null or GSTP1 IIe/IIe105 polymorphisms known to endogenously produce the lowest Phase II enzyme levels responded best to BSE (34).

# **PRELIMINARY STUDIES:**

Administering BSE to allergic subjects was first performed in a recent NIH sponsored study by [name] and colleagues at the University of California, Los Angeles, a partnering institution to the VAGLAHS. Subjects with cat allergy through skin testing diagnosed allergic rhinitis were challenged with 300µg DEP (equivalent to daily PM exposure levels on LA freeway) then underwent 4 weeks of washout, followed by daily BSE administered as a single oral morning dose (11umol sulforaphane equivalent to that formed from consuming 100 to 200 grams of broccoli) for four days. The diesel exhaust particle challenge was repeated after BSE consumption. The average nasal white blood cell counts increased by at least 4 fold (p<0.0005) within 24 hours post-DEP exposure and there was significant attenuation of cell count post-DEP exposure when patients were given daily BSE for four days prior to DEP challenge (p<0.01 at 6 hours and p<0.0001 at 24 hours following DEP challenge). There was no correlation between the inflammatory response and the presence of GSTM1 null orGSTP1 IIe/IIe105 polymorphisms (35). Failure to determine a statistically significant difference in response among the genetic polymorphisms may have been due to the low subject number.

We are proposing a double blinded randomized placebo controlled study to investigate the effectiveness of BSE on nasal health among US veterans with a diagnoses seasonal grass allergic rhinitis in an urban environment where DEP levels are high.

During the study, GST genotype data will be collected in order to obtain data for future exploratory analysis.

# **RESEARCH DESIGN AND METHODS**

# **Objectives:**

Primary Objective:

To conduct a double-blind, randomized, placebo-controlled trial to compare clinical measurements for allergic rhinitis following *Timothy, Bermuda or Johnson* grass allergen (phleum pretense, *cynodon dactylon, or songhum halepense*) challenge before and after initiation of BSE supplementation. Clinical measurements will be derived from the total nasal symptoms score (TNSS) and peak nasal inspiratory flow (PNIF).

# Secondary Objectives:

To conduct a randomized controlled trial to compare biomarker measurements for allergic rhinitis following grass allergen challenge before and after initiation of BSE supplementation. Biomarkers will include the following inflammatory cytokines: Interleukin 4, Interleukin 5, Interleukin 13 along with Tryptase and Eosinophil cationic protein (ECP) obtained through polyurethane sponges placed into both nostrils.

To conduct an exploratory genetic analysis of the 3 glutathione S-transferase (GST) genes (GSTM1, GSTT1, and GSTP1) for future investigation into how genetic polymorphisms effect the response to BSE supplementation in atopic disorders.

# **Overview of Study Design**

The proposed study is a double-blind, randomized, placebo-controlled trial consisting of four arms. A total of *190* subjects diagnosed with grass (p. pretense, *c. cynodon, and/or s songhum*) specific allergic rhinitis will be randomly assigned to one of four groups:

- 1. nasal corticosteroid + Placebo tablet
- 2. placebo nasal spray + Placebo tablet
- 3. nasal corticosteroid + Avmacol®
- 4. placebo nasal spray + Avmacol®

Avmacol is a supplement that supports sulforaphane production by providing glucoraphanin and an active myrosinase enzyme via our Sulforaphane Production System. Subjects will be given 4 tablets to take with their evening meal.

Following consent, a list of antioxidant foods (including sulforaphane containing foods) and prohibited medications to avoid will be given to all subjects then subjects will be scheduled for visit 1 within <20 days.

At visit 1, Subjects will undergo epicutaneous hypersensitivity skin testing to grass allergens prevalent in southern California: Johnson Grass (Sorghum Halepense), Bermuda Grass (Cynodon Dactylon), and Timothy Grass (Phleum Pretense), along with dog, cat and perennial allergens: dust mite (dermatophagoides pteronyssinus, dermatophagoides farina), and common mold allergens (alternaria, aspergillus, cladosporium, and penicillium) (36). Subjects with positive skin test results to one or more grass allergens and either negative skin test to perennial allergens (dust mite or mold) or positive tests to perennial allergens (dust mite or mold) without a correlating clinical history consistent with perennial allergic rhinitis will undergo grass allergen nasal provocation testing. Subjects with a positive skin test to cat or dog and clinical symptoms consistent with cat or dog triggered allergic rhinitis will be asked to avoid cats and or dogs for the entire study. For subjects who have an epicutaneous allergen skin or blood test on file completed by the VA Allergy Clinic within <1 year that confirms a positive to grass pollens the results will be used to proceed onto the up-dosing nasal challenge. Subjects experiencing a positive nasal provocation test defined by a total nasal symptom score (TNSS) over 7, or PNIF is reduced by  $\geq$  50% from baseline redaing will be tested for serum GSTM1 polymorphism and baseline sulforaphane levels and will proceed to visit 2. Subjects failing to mount a positive response with the highest concentration (10,000 BU/cc for p. phleum and c. cynodon, or 1:100 w/v for s. sorghum) will be withdrawn from the study...

Nasal challenge will repeat at visit 2, two weeks after visit 1, and visit 3, 3 weeks after beginning intervention at visit 2. This challenge was developed and perfected by Guy W. Scadding PhD and colleagues and showed reproducibility in a 2012 study (36). Prior to and following each challenge, subjects will undergo spirometry. Challenges will not be performed in patients with forced expiratory volume in 1 second (FEV1) values less than 70%. The visit 1 nasal challenge will be considered a graded up-dosing challenge needed to determine the dose used at visits 2 and 3.

At visit 2 (2 weeks following visit 1) and visit 3 (5 weeks following visit 1), subjects will undergo a single nasal allergen challenge with the effective dose determined during the up-dosing challenge at visit 1. Total nasal symptom score and peak nasal inspiratory flow will be recorded throughout all nasal challenge procedures.

Biomarkers collected through sponges placed in both nasal passages during the challenge will include IL4, IL5, IL13, eosinophil cationic protein and tryptase. At the end of visit 2, patients will be randomized and will be instructed to begin the following evening, to return in 3 weeks for another nasal challenge.

Throughout the study, serum sulforaphane levels for each subject will be checked at visits 1, 2 and 3 to monitor adherence.

All study procedures will be conducted at the VAGLAHS. Subjects will be assigned an appointment day and appointment time for each scheduled visit. All appointments will be at approximately the same time of the day for all subjects to avoid diurnal variation.

Figure 1. Overview of Study Procedures

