challenge. For c. cvnodon (Bermuda grass), dosing will start at 30 BU/ml and will continue with the following concentrations until a TNSS score reaches 7 or greater or PNIF is reduced by >50% from baseline reading: 300, 1000, 3000 and 10,000 BU/ml. For p. pretense(Timothy grass), dosing will start at 300 and will continue with the following concentrations until a TNSS score reaches 7 or greater or baseline PNIF is reduced by > 50% from baseline reading: 1,000,3,000,10,000 and 100,000 BU/ml. For s. sorghum (Johnson grass) dosing will start at 1:200,000 and will continue with the following concentrations until a TNSS score reaches 7 or greater or baseline PNIF is reduced by > 50% from baseline reading: 1:20,000, 1:2000, 1:200, and 1:20 w/v. Subjects will receive three sprays equivalent to 100 µl for each concentration into each nostril using an atomizer device, part of the standardized equipment at VAGLAHS for patients requiring nasal sprays during procedures applied every 10 minutes until maximal concentration or a TNSS score of 7 or PNIF reduction by  $\geq$  50% from baseline reading is achieved. Prior to subsequent challenges at visit 2 and 3, nasal lavage (SinusRinse) will be performed. A baseline PNIF and TNSS will be recorded 30 minutes following nasal layage for visits 2 and 3. Nasal challenge with 100 µl of the final dose achieved at visit 1 will then be applied into each nostril. The PNIF and TNSS will be recorded following challenge at 5, 15, 30 minutes following challenge and then at 1 hour, continuing to record each hour for 4 hours. During these intervals, nasal sponges (Plastocell & Co.) will be applied into each nostril onto the nasal mucosa, beyond the nasal vestibule, and alongside the inferior turbinate with the use of a crock forceps (Phoenix surgical instruments, Harlow, UK) and a Thuddicum's nasal speculum (Phoenix surgical instruments, Harlow, UK). After two minutes of placement, the sponges will be removed and then added to 2 ml centrifuge tubes with indwelling .22µm cellulose acetate filters (Costar Spin-X, Corning, NY, USA) and placed immediately into ice before centrifuging within the hour. The liberated fluid will then be freezed at -80° until analysis occurs.

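### Visit 1 challenge rules conflict: the Timothy maximum differs tenfold, the Johnson maximum is not a dosing step, and a TNSS of exactly 7 can have no stated outcome

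*Combined protocol and SAP*

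**What the plan says.** Two sections of the combined protocol and SAP set the visit 1 up-dosing rules.

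- **Overview of Study Design (visit 1).** It refers to a "positive nasal provocation test defined by a total nasal symptom score (TNSS) over 7", or a PNIF fall of at least 50%. It also holds the only withdrawal rule for non-response: "Subjects failing to mount a positive response with the highest concentration" leave the study. That concentration is spelled out as the "highest concentration (10,000 BU/cc for p. phleum and c. cynodon, or 1:100 w/v for s. sorghum".
- **Procedures performed (Nasal Challenge).** This section gives a five-step ladder for each grass. Bermuda runs from 30 to 10,000 BU/ml. Timothy starts at 300 and continues through "1,000,3,000,10,000 and 100,000 BU/ml". Johnson starts at 1:200,000 and continues through "1:20,000, 1:2000, 1:200, and 1:20 w/v". Dosing goes on "until a TNSS score reaches 7 or greater", or until the PNIF criterion is met or the ladder ends. At visits 2 and 3, 100 microlitres of the "final dose achieved at visit 1 will then be applied into each nostril".

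Procedures at Each Visit, Study Schedule and the sample size text all require a positive challenge, but none gives a threshold. No section says which rule governs.

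**The concern.** The Overview is the only place that says who is positive and who is withdrawn for non-response. Procedures performed is the only place that gives the dosing steps. Staff have to use both, and the two do not fit together. At stake are eligibility for randomisation and the allergen dose each subject receives at three visits, including the two at which the primary TNSS endpoint is measured. Two staff members could handle identical subjects differently and each be following a written instruction.

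**Working it through.** **Maximum concentrations, side by side** (1 cc = 1 ml)

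| Grass | Overview maximum | Top of dosing ladder | Overview value on ladder? | Ratio |
|---|---|---|---|---|
| Bermuda | 10,000 | 10,000 | yes | 1 |
| Timothy | 10,000 | 100,000 | yes, but not the top step | 100,000 / 10,000 = 10 |
| Johnson | 1:100 | 1:20 | no (falls between 1:200 and 1:20) | (1/20) / (1/100) = 5 |

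Timothy is a direct contradiction: a subject negative at 10,000 BU/ml cannot be both withdrawn and dosed again. A stray zero is unlikely, because 10,000 appears on the ladder as a separate step before 100,000. Johnson is a mismatch. The ladder can be run and a subject negative at 1:20 can be withdrawn, but not at the concentration the Overview names.

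**Timothy dose at visits 2 and 3.** The volume is 100 microlitres per nostril, so 0.1 ml × 2 = 0.2 ml.
- Overview maximum: 0.2 × 10,000 = 2,000 BU per visit.
- Ladder maximum: 0.2 × 100,000 = 20,000 BU per visit.

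**Timothy cumulative dose at visit 1**
- Sum of concentrations to 10,000: 300 + 1,000 + 3,000 + 10,000 = 14,300.
- Sum to 100,000: 14,300 + 100,000 = 114,300.
- Ratio: 114,300 / 14,300 = 7.99, whatever volume is given at each step.

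The absolute totals depend on how "Subjects will receive three sprays equivalent to 100" microlitres per nostril is read.
- 100 microlitres in total per nostril (0.2 ml per step): 2,860 against 22,860 BU.
- 100 microlitres per spray (0.1 × 3 × 2 = 0.6 ml per step): 8,580 against 68,580 BU.

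**TNSS of exactly 7.** The score adds four symptoms rated 0 to 3, so 7 is attainable and is the lowest score that stops dosing. The table applies the stop rule from Procedures performed and the positive and withdrawal rules from the Overview, for a PNIF fall under 50%.

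| TNSS | Below the top step | At the top step |
|---|---|---|
| 6 | next dose | withdrawn |
| 7 | dosing stops; not positive; withdrawal rule does not apply | withdrawn |
| 8 | positive | positive |

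With a PNIF fall of 50% or more the subject is positive at any of these scores. Across all 18 combinations (TNSS 6, 7, 8; PNIF fall 40%, 50%, 60%; below or at the top step), only one has no outcome: TNSS 7 with a PNIF fall under 50%, below the top step.

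**Recruitment if the lower maxima are adopted.** The plan's own chain reproduces with its rounding: 475 × 0.5 = 237; 237 × 0.80 = 190; 190 × 0.80 = 152 completers. The power calculation uses 36 per arm, so 4 × 36 = 144 completers.
- Break-even for 144: 144 / 0.80 = 180 randomised; 180 / 237 = 0.7595, so a positive-challenge rate of about 76.0%.
- Against the stated target of 152 there is no slack, because 190 / 237 is already about 80%.
- At 75% (an illustrative assumption): 237 × 0.75 = 177.8 randomised and 177.8 × 0.80 = 142.2 completers. Keeping 190 randomised would need 190 / 0.75 / 0.5 = 506.7, about 507 screened.

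**The case against.** The strongest reply is that one section is an overview and the other is the working instruction. Staff would follow the ladder, and the Overview's figures are a loose parenthesis to be tidied. That is plausible as a habit, but the document has no precedence clause. The Overview is also not redundant, since it alone defines positive and states withdrawal for non-response.

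On the score of 7, Procedures at Each Visit and Study Schedule let only positive subjects continue, which implies that a subject stopped at 7 does not. This has some force: what is missing is an explicit disposition, and a reader could infer one. But the inference would drop a subject whom the stop rule treats as having responded, before the remaining doses were tried. The opposite inference, that the stop criterion is the response criterion, is equally available.

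The Johnson point is minor in practice, as the ladder can be run.

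Several limits also stand. No section states a safe allergen maximum, so a safety consequence is possible but not shown. Safeguards exist: graded dosing with stopping criteria, spirometry with an FEV1 floor, exclusion of prior anaphylaxis to environmental allergens or an unknown trigger and of uncontrolled asthma, epinephrine and a crash cart in the clinic, and DSMB authority to stop. The recruitment cost arises only if the assumed 80% positive rate was set with the higher maxima in mind, which the plan does not say. Counting a TNSS of 7 as positive could raise that rate.

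**Conclusion.** The concern holds. This is an internal inconsistency in decision thresholds, and it should be corrected. The Timothy maxima differ tenfold, and cumulative visit 1 exposure differs 8.0-fold. A subject who first responds at 100,000 BU/ml is either withdrawn or receives that concentration at all three visits. The Johnson top step is 5 times the concentration the Overview names. The TNSS gap affects only a score of exactly 7 with a PNIF fall under 50%, below the top step. Bermuda is consistent, and carrying the visit 1 dose forward to visits 2 and 3 is clear.

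The decision is made before randomisation, and each subject has the same dose at visits 2 and 3, so the arm comparison and the power calculation are not directly affected. The documents give no frequencies for these subgroups, so the number of subjects affected cannot be estimated.

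**What to change.** The clinical team should choose one maximum per grass and state it identically in Overview of Study Design and Procedures performed. Bermuda stays at 10,000 BU/ml.

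- **Option 1: keep the ladders.** Change the Overview to 100,000 BU/ml for Timothy and 1:20 w/v for Johnson. This costs wording only.
- **Option 2: lower the ladders.** Delete the 100,000 BU/ml Timothy step. For Johnson, either replace the 1:20 step with 1:100, or end at 1:200 and change the Overview to 1:200. This is also wording, but it may lower the positive-challenge rate, so the screening number should be rechecked against the break-even above.

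The documents give no basis for preferring one option, because no safe limit is stated.

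Under either option, redefine a positive test in the Overview as a TNSS of 7 or more, or a PNIF fall of at least 50%, so that every subject whose dosing stops on a response is positive. This costs wording only.

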# **Study Population**

# General Considerations:

Subjects participating in the study are followed at two VA medical centers and one academic medical center. All subjects are non-smoking male or female US veterans aged 18 years and older with symptoms consistent with seasonal summer allergic rhinitis (rhinorrhea, nasal congestion, postnasal drainage sneezing, and/or nasal or eye pruritus). There will be no exclusion based on gender or ethnic/racial background.

